### 7.3.2. Subgroup Analyses for Primary Endpoint

Subgroups will be formed based on the following participant characteristics and baseline variables for those participants whose data are available:

- ARDS severity: severe ( $\text{PaO}_2/\text{FiO}_2 \leq 100$  mmHg) versus mild/moderate ( $\text{PaO}_2/\text{FiO}_2 > 100$  and  $\leq 300$  mmHg)
- Gender: male or female
- Age group:  $< 18$  years, 18-64 years, or  $\geq 65$  years
- Baseline CRP:  $\leq 100$  mg/L or  $> 100$  mg/L
- D-dimer at baseline:  $\leq 1000$  ng/mL or  $> 1000$  ng/mL
- Ferritin at baseline:  $\leq 300$  ng/mL or  $> 300$  ng/mL
- Race: White/Caucasian, Black/African-American, Asian, American-Indian/Alaska Native, Native Hawaiian/Pacific Islander, or Other
- Ethnicity: Hispanic/Latino, Not Hispanic/Latino, or Other
- Hours of mechanical ventilation at baseline:  $\leq 48$  hours or  $> 48$  hours
- BMI at baseline:  $\geq 30$  or  $< 30$
- Prior or concomitant remdesivir: yes or no
- Prior or concomitant convalescent plasma: yes or no
- Concomitant anticoagulant use: yes or no
- Concomitant corticosteroid use: yes or no
- Prior biologic use: yes or no

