7.2.1.1. Permitted Concomitant Therapy Requiring Caution and/or Action

Participants may receive the following (not inclusive): antiemetics, calcineurin inhibitors, azole fungal prophylaxis, antibiotics, acyclovir prophylaxis, granulocyte-colony stimulating factor, corticosteroid premedications prior to RBC/platelet transfusions, narcotics, and sedatives; however, close monitoring of potential drug-drug interaction effects of these concurrent drugs is warranted.

Use of oral, injected, or implanted hormonal methods of contraception are allowed while on ruxolitinib.

In the presence of potent CYP3A4 inhibitors, there is the possibility of increased exposure to ruxolitinib. Dose adjustment when coadministering ruxolitinib and a potent CYP3A4 inhibitor is only required for participants assigned to the 15 mg BID ruxolitinib/placebo arm; see Section 7.2.1.2 for additional details. No dose adjustment is required for participants

randomized to the 5 mg BID ruxolitinib/placebo arm. See Appendix D for a list of CYP3A4 inhibitors and inducers.

The participant and the treating investigator should be aware of potential signs of overdose of the concomitant medications; in the event of suspected study drug–related toxicity, administration of ruxolitinib should be dose reduced or held according to the treating investigator's judgement.

For additional information, please refer to the IB.

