12.4. Statistical Analyses

12.4.1. Primary and Secondary Analysis

Unless otherwise noted, all statistical comparisons of each ruxolitinib treatment groups will be performed as pairwise comparisons against placebo. See Table 10 for analyses of primary and secondary endpoints.

Endpoint	Statistical Method	Analysis Population	Primary (P) or Supportive (S)
Primary Endpoint			
Proportion of participants	Logistic regression with treatment	ITT	Р
who have died due to any cause through Study Day 29.	group, ARDS severity (mild/moderate vs severe), gender (male or female) as fixed covariates, and investigational site as a random effect. Wald test for treatment group regression coefficient = 0. Estimation: Odds-ratio for treatment effect and associated 95% CI.	РР	S
Overall survival up to Day 29 determined from the date of randomization until death due to any cause	Inference: Cox proportional hazards model including treatment group, ARDS severity (mild/moderate vs severe), and gender (male or female) as fixed covariates, and investigational site as a random effect. Estimation: Kaplan-Meier.	ITT	S

 Table 10:
 Analyses of Primary and Secondary Endpoints

Endpoint	Statistical Method	Analysis Population	Primary (P) or Supportive (S)
Secondary Endpoint			
Improvement in the	Proportional odds model including	ITT	Р
COVID-19 ordinal scale at Day 15 and 29	treatment group, ARDS severity (mild/moderate vs severe), and gender (male or female) as fixed covariates, and investigational site as a random effect.	РР	S

Table 10: Analyses of Primary and Secondary Endpoints (Continued)

All other secondary endpoints will be tabulated by summary statistics.

The primary endpoint will also be compared between the treatment groups within each of the following subgroups. In the event that any subgroup category has fewer than 10 participants, the subgroup in question may be excluded.

- ARDS severity: mild/moderate versus severe
- Gender: male or female
- Age group: < 18 years, 18-64 years, or ≥ 65 years
- Baseline CRP: $\leq 100 \text{ mg/L or} > 100 \text{ mg/L}$
- D-dimer at baseline: $\leq 1000 \text{ ng/mL or} > 1000 \text{ ng/mL}$
- Ferritin at baseline: $\leq 300 \text{ ng/mL or} > 300 \text{ ng/mL}$
- Race: White/Caucasian, Black/African-American, Asian, American-Indian/Alaska Native, Native Hawaiian/Pacific Islander, or Other
- Ethnicity: Hispanic/Latino, Not Hispanic/Latino, or Other
- Hours of mechanical ventilation at baseline: ≤ 48 hours or > 48 hours

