### **4.2.2. Prior and Concomitant Medication**

Prior medication is defined as any nonstudy medication started before the first dose of ruxolitinib/placebo.

Concomitant medication is defined as any nonstudy medication that is started accordingly:

- Before the date of first administration of ruxolitinib/placebo and is ongoing throughout the study or ends on/after the date of first study drug administration.
- On/after the date of first administration of ruxolitinib/placebo and is ongoing or ends during the course of study.

A prior medication could also be classified as "both prior and concomitant medication" if the end date is on or after the first dose of ruxolitinib/placebo. In the listing, it will be indicated whether a medication is only prior, only concomitant, or both prior and concomitant.

For the purposes of analysis, all medications will be considered concomitant medications unless the medications can unequivocally be defined as not concomitant.

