#### 6.1.2. Baseline Disease Characteristics and Disease History

The following baseline disease characteristics will be summarized for the ITT population: predefined coexisting disorders, baseline SOFA score, baseline COVID-19 9-point ordinal scale clinical status, baseline ARDS severity (severe [ $\text{PaO}_2/\text{FiO}_2 \leq 100$ ] vs mild/moderate [ $\text{PaO}_2/\text{FiO}_2 > 100$  and  $\leq 300$  mmHg]), ARDS severity at randomization, time (in hours) from start of mechanical ventilation to randomization, time (in days) from initial diagnosis to randomization, time (in days) from hospital admission to randomization, baseline CRP ( $\leq 100$  mg/L or  $> 100$  mg/L), baseline D-dimer ( $\leq 1000$  ng/mL or  $> 1000$  ng/mL), baseline ferritin ( $\leq 300$  ng/mL or  $> 300$  ng/mL), BMI at baseline ( $\geq 30$  or  $< 30$ ), prior or concomitant remdesivir, prior or concomitant convalescent plasma, prior or concomitant corticosteroid, concomitant anti-coagulant, prior biologic, prior or concomitant neutralizing antibodies, and prior or concomitant corticosteroid with prior or concomitant remdesivir.

Time from initial diagnosis will be calculated as follows:

$$\text{Time since diagnosis (days)} = (\text{date of randomization} - \text{date of diagnosis} + 1).$$

Time from start of mechanical ventilation will be calculated as follows:

$$\text{Time from start of mechanical ventilation (hours)} = (\text{date and time of randomization} - \text{date and time of intubation}).$$

Time from hospital admission to randomization will be calculated as follows:

$$\text{Time from hospital admission (days)} = (\text{date of randomization} - \text{date of hospital admission} + 1).$$

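### Four mortality subgroups in the SAP (remdesivir, convalescent plasma, anticoagulant, corticosteroid) are defined partly by treatment started after randomization, so their within-subgroup odds ratios can be biased

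*SAP*

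**What the plan says.** SAP 7.3.2 introduces the subgroups for 28-day mortality with "Subgroups will be formed based on the following participant characteristics and baseline variables". Most entries are fixed at entry: ARDS severity, gender, age, baseline CRP, D-dimer, ferritin, BMI, and hours ventilated at baseline. Biologics are limited to prior use. Four entries are not limited in this way: remdesivir and convalescent plasma, each prior or concomitant, then "Concomitant anticoagulant use: yes or no" and "Concomitant corticosteroid use: yes or no".

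SAP 4.2.2 gives concomitant medication two limbs. One covers drugs started before first dose and still running at or after it. The other covers drugs started "On/after the date of first administration of ruxolitinib/placebo and is ongoing or ends during the course of study". Where timing is unclear, "all medications will be considered concomitant medications unless the medications can unequivocally be defined as not concomitant".

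SAP 6.1.2 places similar variables in the baseline disease table: "prior or concomitant remdesivir, prior or concomitant convalescent plasma, prior or concomitant corticosteroid, concomitant anti-coagulant, prior biologic". SAP 4.1.3 defines baseline as before first administration.

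Protocol 7.2.1 has medications recorded from randomization through Day 29, the same window as the mortality endpoint. Protocol 12.4.1 states the form of the comparison: "The primary endpoint will also be compared between the treatment groups within each of the following subgroups". Its own list does not include these four; SAP 11.2.1 shows that SAP Amendment 1 added them.

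**The concern.** A participant first given a corticosteroid on Day 20 is classed as a user. One who dies on Day 3 before any could be started is classed as a non-user. Status is settled during the same 28 days in which death is counted.

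Comparing arms within such categories keeps the protection of randomization only if study drug affects neither survival nor the starting of the other drug. The trial exists because ruxolitinib is expected to affect survival. The documents also show routes by which it could affect starting:

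- **Corticosteroid.** Protocol 7.2.1.1 permits "corticosteroid premedications prior to RBC/platelet transfusions", and this would count as corticosteroid use. Protocol 5.6 describes dose-dependent thrombocytopenia and anemia on ruxolitinib, though in myelofibrosis with longer and generally higher dosing.
- **Anticoagulant.** Protocol 9.4.3.4 ties anticoagulation to thromboembolic risk, monitored partly by D-dimer, and change in D-dimer is an exploratory endpoint.

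What is at stake is interpretation. Readers will ask whether the ruxolitinib effect depends on background steroids or remdesivir, and a difference between the two odds ratios could look like effect modification when it only reflects who lived, or worsened, long enough to be given the drug.

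**Working it through.** The plan gives no figure on this point, so there is none to reproduce. The check is an illustration.

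**Inputs from the documents.** Mortality of 40% on ruxolitinib and 60% on placebo (SAP 3.3), so the overall odds ratio is (0.4/0.6)/(0.6/0.4) = 0.444. Final sample 211 at 2:2:1 (SAP 3.3, 3.1): 211 × 2/5 ≈ 84 per ruxolitinib arm and 211/5 ≈ 42 on placebo.

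**Assumed inputs.** Constant hazards over D = 28 days; a concomitant drug with no effect on death; a start hazard s per day; a share b already on the drug at baseline.

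**Formulas, per arm.** With m the mortality and l = −ln(1−m)/D:

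- P(non-user, dead) = (1−b) · l/(l+s) · (1 − e^(−(l+s)D))
- P(non-user, alive) = (1−b) · e^(−(l+s)D)
- P(user, dead) = m − P(non-user, dead)
- P(user, alive) = (1−m) − P(non-user, alive)
- SE of a log odds ratio = square root of the sum of 1/(expected cell count)

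**One case in full** (m = 0.4 vs 0.6, s = 0.05 in both arms, b = 0). The death hazards are 0.01824 and 0.03272 per day.

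| Arm | Non-user dead | Non-user alive | User dead | User alive |
|---|---|---|---|---|
| Ruxolitinib | 0.2278 | 0.1480 | 0.1722 | 0.4520 |
| Placebo | 0.3566 | 0.0986 | 0.2434 | 0.3014 |

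Users: (0.1722/0.4520)/(0.2434/0.3014) = 0.472. Non-users: (0.2278/0.1480)/(0.3566/0.0986) = 0.426. Users make up 62% of the ruxolitinib arm and 54% of placebo, although the start rate is the same.

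**All cases** (ruxolitinib value first):

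| Mortality | Starts per day | b | OR, users (SE of log) | OR, non-users (SE of log) | Overall OR |
|---|---|---|---|---|---|
| 60% vs 60% | 0.05 vs 0.05 | 0 | 1.00 (0.51) | 1.00 (0.68) | 1.00 |
| 40% vs 60% | 0.05 vs 0.05 | 0 | 0.472 (0.52) | 0.426 (0.66) | 0.444 |
| 40% vs 60% | 0.05 vs 0.05 | 0.5 | 0.452 (0.43) | 0.426 (0.94) | 0.444 |
| 60% vs 60% | 0.025 vs 0.05 | 0 | 0.896 (0.56) | 0.633 (0.63) | 1.00 |
| 60% vs 60% | 0.025 vs 0.05 | 0.5 | 1.031 (0.44) | 0.633 (0.89) | 1.00 |
| 60% vs 60% | 0.05 vs 0.025 | 0 | 1.116 (0.61) | 1.581 (0.57) | 1.00 |
| 60% vs 60% | 0.03 vs 0.02 | 0 | 1.049 (0.68) | 1.193 (0.50) | 1.00 |

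In this model, subgroups fixed at baseline return the overall odds ratio in both categories, so the shifts are not non-collapsibility.

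**Starts that depend on severity.** A second model also has no drug effect on death. In each arm 40% use the drug before first dose (60% mortality). The other 60% split equally into worsening (75% mortality) and not worsening (45%). Later starts in these two groups are 60% and 20% on placebo, and half that (30% and 10%) on ruxolitinib.

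- Users, ruxolitinib: share 0.4 + 0.3×0.3 + 0.3×0.1 = 0.52; deaths 0.24 + 0.0675 + 0.0135 = 0.321; mortality 0.617.
- Users, placebo: share 0.4 + 0.18 + 0.06 = 0.64; deaths 0.24 + 0.135 + 0.027 = 0.402; mortality 0.628.
- Non-users: 0.279/0.48 = 0.581 on ruxolitinib; 0.198/0.36 = 0.55 on placebo.

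The odds ratios are 0.95 for users and 1.14 for non-users. Halving the starts now pushes the non-user odds ratio above 1, where the first model put it at 0.63.

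**The case against.** **The survival route is small.** At the plan's own effect, the log odds ratio moves by +0.06 (users) and −0.04 (non-users) against standard errors of 0.52 and 0.66. This stands.

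**The larger shifts need an assumed arm difference in initiation.** No document gives a figure for one, treatment is double-blind, and the sign changes with the model. The mechanism evidence is also mixed: Protocol 5.6 says the hematopoietic effects are less pronounced in several non-myelofibrosis populations, and Protocol 5.3 reports blood counts improving on ruxolitinib in secondary HLH. This stands as a limit on size and direction. It does not make the categories baseline ones.

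**Precision is poor anyway.** With halved initiation and b = 0, the non-user shift of 0.46 is about 0.7 of its standard error; with half already on the drug, about 0.5. The contrast between users and non-users is 0.35 to 0.49 on the log scale, against a standard error of about √(0.56² + 0.63²) = 0.84 to √(0.44² + 0.89²) = 0.99. This is true, but a confidence interval does not show a systematic error.

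**The text does not call every item baseline.** The lead-in also mentions participant characteristics, the four are openly labelled concomitant, SAP 7.3.2 names no model for the subgroups, and the forest plot title in SAP Appendix A does not mention them. This is fair on wording. SAP 6.1.2 does list such variables under baseline characteristics, and comparing arms within subgroups is the evident purpose.

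**Conclusion.** The concern holds. Followed as written, the SAP conditions a randomized comparison on status that can be settled after randomization, in four of its mortality subgroups. The bias is zero if study drug affects neither survival nor initiation of the drug in question; otherwise it can go in either direction. In the illustrations it ranges from negligible (0.472 and 0.426 around 0.444) to an apparent non-user odds ratio of 0.63 or 1.58 when the truth is 1.00. Those figures rest on assumed start rates and constant hazards, and the real size may be small. All shifts shown are below one standard error at 211 participants. The primary analysis and its Type I error are untouched. The change should be made because it is cheap and removes a known source of misreading; it is not a condition for the trial's main conclusion.

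**What to change.** - **Anticoagulant and corticosteroid:** define as started before, and ongoing at, randomization (yes/no).
- **Remdesivir and convalescent plasma:** define as started on or before randomization within the 14-day collection window (yes/no).
- **Date rule:** for these subgroups, replace the default to concomitant. For example, a same-day start without a clock time counts as yes, and a start date too incomplete to place before or after randomization is missing for that subgroup. The same-day rule lets in a few later starts, which is a small leak.
- **Anchor:** state that randomization is used because the arms are comparable at that point, and note that SAP 4.1.3 anchors baseline on first dose for treated participants.
- **Later use:** report descriptively by arm only.
- **SAP 6.1.2:** use the same definitions in the baseline table.

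The cost is SAP wording plus one date rule, since SAP 4.1.5 has none for medication start dates. Under Protocol 7.2.1, capture before randomization is limited to COVID-19 and ARDS treatments within 14 days, while everything from randomization on is recorded. Use ongoing at randomization is therefore derivable; an anticoagulant stopped earlier may not be. The yes categories will be smaller.

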### 7.3.3. Sensitivity and Supportive Analyses for Primary Endpoint

A sensitivity analysis will be conducted in the ITT population, in which nonevaluable participants will be treated as deaths. The primary endpoint will be analyzed using the PP population as a sensitivity analysis to the ITT analysis. In addition, a tipping point analysis will be performed to measure the robustness of the treatment effect under assumptions for participant dropout. The tipping point analysis will use an unstratified 2-sample test of proportion, modifying dropouts within the compared ruxolitinib treatment group as having died and placebo participants as having lived to determine if and at what point in this imputation a statistically significant treatment effect under the base assumptions will lose statistical significance.

Analyses related to the primary endpoints are delineated in [Table 3](#).

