### **3.2. Control of Type I Error**

The Type 1 error level for the primary endpoint is 1-sided 2.5%. A fixed sequence testing procedure will be used to test the 15 mg BID group against placebo first, and if that is significant, then the 5 mg BID group will be tested against placebo. If the test for the 15 mg BID group is not significant, the 5 mg BID group will not be tested.

If the null hypotheses are rejected for both ruxolitinib treatment groups when compared with placebo for the primary endpoint, then a statistical comparison will be performed between the 2 ruxolitinib groups.

No multiplicity adjustments will be applied to other endpoints. Secondary efficacy variables will be tested at a 0.05 level and will use a 2-sided test. All exploratory variables will use a 2-sided, 5% alpha with no adjustment for multiplicity.

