### **3.3. Sample Size Considerations**

The primary endpoint of this study is the proportion of participants who die due to any cause through Study Day 29. The primary endpoint will be tested for each ruxolitinib treatment group using a logistic regression model including treatment (ruxolitinib vs placebo) and ARDS severity (severe [ $\text{PaO}_2/\text{FiO}_2 \leq 100$ ] vs mild/moderate [ $\text{PaO}_2/\text{FiO}_2 > 100$  and  $\leq 300$ ]) as fixed covariates and investigational site as a random (intercept) effect. For placebo randomized 2:2:1 (ruxolitinib 5 mg BID:ruxolitinib 15 mg BID:placebo) assuming a 40% mortality rate for ruxolitinib versus 60% for placebo, a sample size for a pairwise comparison of 100 placebo and 200 ruxolitinib participants (with 500 participants total) will achieve approximately 83% power to detect a statistically significant difference with a nominal 1-sided Type I error of 1.436968%.

Estimated power and Type I error for various scenarios, based on a simulation study of 1000 study replications, are provided in [Table 2](#).

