### 7.1. General Considerations

Unless otherwise stated, the strata identified in the randomization process will be used in all efficacy analyses. For statistical analyses of the primary and secondary endpoints, separate models will be fit for the ruxolitinib 5 mg BID versus placebo and ruxolitinib 15 mg BID versus placebo comparisons.

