### 7.3. Analysis of the Primary Efficacy Parameter

#### 7.3.1. Primary Efficacy Analysis

The primary endpoint, 28-day mortality, will be tested using a logistic regression mixed model including treatment group (specific ruxolitinib treatment group vs placebo) and ARDS severity (severe vs mild/moderate) as fixed covariates and investigational site as a random (intercept) effect. The estimation technique for the model fit will use the residual pseudo-likelihood with a subject-specific expansion ([SAS Institute 2013](#)) approach and will be implemented in the SAS GLIMMIX procedure. If the model is not estimable due to convergence issues, a fixed effects logistic regression will be performed instead, excluding investigational site from the model. The Wald test for the treatment regression coefficient will test the primary endpoint.

An estimate and 95% CI for the difference in proportions for 28-day mortality for the 2 treatment groups will be provided. The estimate will be based on the logistic regression model ([Ge et al 2011](#)) using an average of the difference between the 2 levels of the fixed factor (ARDS severity) weighted for the proportion of the study population within each of the 2 levels

of the fixed factor. The delta method will be used to derive the variance estimate, based on the functional form of the estimate  $\gamma^T g(\underline{b})$  using  $\gamma = (\gamma_1, \gamma_2)$  where

- $\gamma_1$  is the proportion of participants in the  $b_2 = 0$
- $\gamma_2$  is the proportion of participants in the  $b_2 = 1$

$\underline{b}$  is the vector of the logistic regression coefficients, and

$$g(\underline{b}) = \frac{1/1 + \exp(\underline{\gamma}^T \underline{b}_0 - b_1) - 1/1 + \exp(\underline{\gamma}^T \underline{b}_0)}{1/1 + \exp(\underline{\gamma}^T \underline{b}_0 - b_1 - b_2) - 1/1 + \exp(\underline{\gamma}^T \underline{b}_0 - b_2)} .$$

Point estimates and 95% CIs will also be provided for the model-based mortality rates using the delta method.

Participants who are lost to follow-up before Day 29 will not be evaluable for this endpoint. As the participants begin the study intubated, those who remain hospitalized are unlikely to be lost to follow-up, but reasonable efforts will be made to track down missing participants.

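### The tipping-point analysis uses a simpler test than the primary model, so it can start from a different significance result than the one it is meant to stress.

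*SAP*

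**What the plan says.** **Primary test (SAP 7.3.1).** Day 29 mortality "will be tested using a logistic regression mixed model including treatment group (specific ruxolitinib treatment group vs placebo) and ARDS severity" as fixed terms, with site as a random intercept. "The Wald test for the treatment regression coefficient will test the primary endpoint". If that model does not converge, "a fixed effects logistic regression will be performed instead, excluding investigational site from the model"; severity stays in.

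**Tipping point (SAP 7.3.3).** "The tipping point analysis will use an unstratified 2-sample test of proportion". Ruxolitinib dropouts are switched to deaths and placebo dropouts to survivors, to find whether and where "a statistically significant treatment effect under the base assumptions will lose statistical significance". The section does not say which version of the two-sample test is meant. It does not say whose significance counts as the base result, or what happens if this test and the Wald test disagree before anything is switched.

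**General rule (SAP 7.1).** Unless an analysis states otherwise, "the strata identified in the randomization process will be used in all efficacy analyses".

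**Other sensitivity analyses (SAP Table 3).** Every logistic-regression row keeps treatment, severity and random site. That includes the row counting participants lost before Day 29 as deaths. The tipping point is not in that table.

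**The concern.** A tipping-point analysis reports how many unfavourable dropout outcomes a positive claim survives. The count is easy to read only if step zero is the claim itself.

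Here the claim comes from one test and the count from another. If the Wald test is significant and the two-sample test is not, the claim looks tipped with no dropout changed. If the two-sample test starts further beyond the boundary than the Wald test, the count overstates robustness.

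This matters somewhat more than usual because the final analysis has 211 participants rather than 500, so results near the boundary are likely. Participants lost before Day 29 are not evaluable in the primary analysis. The tipping point is then one of only two planned analyses that vary their outcomes.

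**Working it through.** **1. The plan's own power figure.** SAP 3.3 gives about 83% for 100 placebo versus 200 ruxolitinib, 60% versus 40%, "with a nominal 1-sided Type I error of 1.436968"% (z = 2.187).

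- Pooled rate: (60 + 80)/300 = 0.4667. Null SE: √(0.4667 × 0.5333 × (1/100 + 1/200)) = 0.0611. Alternative SE: √(0.24/100 + 0.24/200) = 0.0600.
- No correction: Φ((0.200 − 2.187 × 0.0611)/0.0600) = Φ(1.106) = 86.6%, matching the simulated 0.868 and 0.872 in SAP Table 2.
- Continuity correction of ½(1/100 + 1/200) = 0.0075: Φ((0.1925 − 0.1336)/0.0600) = Φ(0.981) = 83.7%, matching the stated 83%.

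The documents thus contain figures consistent with both versions of the test, and SAP 7.3.3 does not say which applies.

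**2. The size that will be analysed.** At 2:2:1, 211 × 1/5 ≈ 42 placebo and 211 × 2/5 ≈ 84 per ruxolitinib group. On the level, SAP 3.2 says: "The Type 1 error level for the primary endpoint is 1-sided 2.5"%. Null SE: √(0.2489 × (1/42 + 1/84)) = 0.0943. Alternative SE: √(0.24 × (1/42 + 1/84)) = 0.0926. Power = Φ((0.200 − 1.960 × 0.0943)/0.0926) = Φ(0.164) ≈ 56.5%.

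**3. One data set, three statistics.** Take 26/42 placebo and 36/84 ruxolitinib deaths, a difference of 0.1905.

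- Pooled z = 0.1905/0.0945 = 2.02.
- Continuity-corrected z = (0.1905 − 0.0179)/0.0945 = 1.83.
- Unadjusted Wald z on the log odds ratio = 0.773/0.387 = 2.00.

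The boundary is 1.96, so the test version alone can reverse the starting result.

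**4. Starting disagreement, site omitted.** Simulation of 42 versus 84, 60% versus 40%, half severe and exactly balanced across arms, 8,000 trials per row. The severity-adjusted Wald test is compared with the two-sample z-test. The severity odds ratios are assumptions; the documents give none.

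| Severity OR | Primary-significant trials that start non-significant, pooled test | Same, continuity-corrected | Reverse, pooled (all trials) |
|---|---|---|---|
| 2 | 1.2% | 15.5% | 0.0% |
| 3 | 3.4% | 17.6% | 0.01% (one trial) |
| 4 | 6.6% | 21.8% | 0.0% |

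If severity is instead left to chance, the pooled-test column becomes 5.2%, 8.9% and 12.6%, with the reverse in 2.6-3.4% of all trials. That does not describe this trial, because randomization is stratified by severity.

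**5. Starting disagreement with site effects.** Own code for residual pseudo-likelihood with a random site intercept (not SAS), against the pooled test; 10 sites, 1,000 trials per row. Site SD is on the logit scale and is assumed.

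| Severity OR | Site SD | Primary only significant | Unstratified only significant | Total discordant |
|---|---|---|---|---|
| 2 | 0 | 0.4% | 0.6% | 1.0% |
| 2 | 0.5 | 2.3% | 1.4% | 3.7% |
| 2 | 1 | 8.3% | 3.4% | 11.7% |
| 4 | 0 | 3.8% | 0.2% | 4.0% |
| 4 | 1 | 8.5% | 2.3% | 10.8% |

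A further run imposed permuted blocks of five within each site-by-severity stratum (block size assumed; 1,500 trials per row). Total discordance was 2.1% (OR 2, SD 0.5), 5.3% (OR 2, SD 1) and 7.5% (OR 4, SD 1), nearly all of it primary only. The 12% is therefore an upper figure.

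**The case against.** A simple two-sample test is a transparent choice for a supportive grid. It depends only on counts, so it does not matter which dropout is switched. It also avoids refitting a mixed model for which the SAP itself foresees convergence failure. With severity balanced and a pooled test, it starts significant in about 93-99% of primary-significant trials, and a mismatch would be visible at step zero. The row counting lost participants as deaths already keeps the primary model. The SAP also expects few losses among those still in hospital. All of this stands, and it makes the point a minor one.

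A reader might infer that the analysis contradicts SAP 7.1. It does not: that rule yields wherever an analysis states otherwise, and SAP 7.3.3 does so by calling the test unstratified.

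A reader might also infer that the analysis cannot answer its own question. That goes too far: it answers it whenever the two tests agree at the start, which is most of the time.

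What remains is that the SAP gives no reason for the departure, does not name the test version, and has no rule for disagreement.

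**Conclusion.** The point holds as a minor weakness of one supportive analysis. The primary test, its Type I error and its estimate are untouched.

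The pooled-test shares of about 1%, 3-4% and 6% assume balanced severity, no site effect and the planning mortality rates. The continuity-corrected range of about 16-22% rests on the same assumptions. The figure of up to about 12% of all trials depends on a site SD of 1, which nothing in the documents supports or excludes. No dropout rate is given, so the tipping point itself, and any error in it, cannot be computed. If the primary result is not significant, or dropout is negligible, the analysis has little role.

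**What to change.** In SAP 7.3.3:

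1. Run the grid with the primary model: treatment, ARDS severity and random site, with the same Wald test and one-sided level. The unimputed step then equals the primary result by construction.
2. Use one model throughout. If the mixed model fails to converge at any step, use the fallback without site at every step, including the unimputed start, so that a change of model is not mistaken for a tipping point.
3. Where only some dropouts are switched, state how they are chosen, for example by averaging over random selections or reporting the range. Once severity and site are in the model, the choice affects the p-value.
4. Report the unimputed result beside the primary p-value.

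If the simple test is kept, the minimum is to name its version, show its unimputed result beside the primary one, and say what is concluded if they disagree.

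The cost is a few sentences and a loop around existing code. The downside is modest extra programming and possible convergence failures, which item 2 handles.
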